10.7.2 Statistical methods

This section provides specifications for preparation of final Statistical Analysis Plan (SAP), which will be issued prior to database lock. Any differences compared to this statistical section should be identified and documented in final SAP. Analysis will be done using SPSS version 21.

10.7.3 Analysis variables

Descriptive Analysis:

- Descriptive analysis of the collected data. All enrolled patients will be included in the safety analysis.
- All quantitative primary and secondary end point variables will be described
- Data from primary and secondary endpoints will be summarized using appropriate summary statistics i.e. n (number of subjects), mean, Standard Deviation (SD), median and range.

Comparative Analysis:

- All tests will be performed on the 5% level of significance.
- Chi² test for unpaired categorical variables.
- Paired t-test to estimate the change in numerical variables throughout the study visits.
- Student t-test to estimate the comparison between the subgroups for the numerical variables.
- *P*-values less than 0.05 will be considered statistically significant

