- Presence of any signs/symptoms of post-operative wound infection such as redness, fever or wound discharge will be recorded (in case of post-operative subjects)
- Safety laboratory tests (including Total Leucocytic count, Liver enzymes (SGOT & SGPT), Total Bilirubin and S. Creatinine)
- The End of Study Form must be completed.

10.3 Variables:

10.3.1 Primary Endpoints:

1- *Primary Safety:*

Incidence of serious/non-serious adverse events

2- *Primary Efficacy:*

- Complete resolution for pelvi-abdominal infection based on pelvi-abdominal ultrasound and others and/or clinical response
- Complete healing of post-operative wounds

10.3.2 Secondary Endpoints:

1- *Secondary Safety:*

- Presence of any signs/symptoms of post-operative wound infection such as redness, fever or wound discharge.
- Change in Total leukocytes count and Liver enzymes (SGOT, SGPT), between baseline (visit 1) to End of study visit (Follow up 2 visit)

-

2- *Secondary Efficacy:*

- Describe complete resolution, improvement, failure or relapse of pelvi- abdominal infection based on pelvi-abdominal ultrasound and others and or clinical response.
- Days for complete healing of post-operative wounds after 8 days of treatment (Follow-up 1 V) & 15 days of treatment (End of study visit) between the 2 groups

10.4 Data Sources:

All visits assessments will be kept in the source files for each patient and in CRF, which will be verified by the CRA responsible.

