10.5.1 Determination of Sample Size

As the primary objective is to assess the safety of oral Ciprodiazole[®] tablets (Ciprofolxacin /Metronidazole) versus currently used Ciprofloxacin Tablets & Metronidazole tablets following IV antibiotics in post-operative period, for pelvi-abdominal surgeries, and based on the previous study "Comparison of Intravenous/Oral Ciprofloxacin Plus Metronidazole Versus Piperacillin / Tazobactam in the Treatment of Complicated Intra-abdominal Infections".^[15] Overall clinical resolution rates were statistically superior for CIP+MET (74%) compared with PIP/TAZO (63%). Mean length of stay was 14 days for CIP1MET and 17 days for PIP/TAZO patients.

So, the following parameters are used to calculate the expected sample of the study:

- Design: non-inferiority
- Sample Size = 312 Subjects (1:1)
- Ciprodiazole Sample Size (Experimental group) = 156 subjects
- Current used regimen Sample Size (Control group) = 156 subjects
- Confidence level 95% (α error = 5%)
- Power = 80%
- Non-Inferiority margin = 2%

10.5.2 Sample Size & Treatment Groups:

Total of 312 Egyptian patients who have pelvi-abdominal infection or started IV antibiotics in post-operative period, for pelvi-abdominal surgeries will be enrolled in the study and randomized, using a computer system, with a ratio of 1:1, into two categories as follows:

1. Group will receive Ciprodiazole[®] tablets; 156 patients
2. Group will receive Ciprofloxacin Tablets & Metronidazole tablets; 156 patients

10.5.3 Randomization:

Subjects will be randomized into the two treatment groups with a balanced ratio of 1:1. Randomization by block Computer-generated randomization lists will be established by Data Management department (DM) of CRO (Nagy Research). The number of patients of the two treatment groups will be balanced (ratio 1:1). (156 Ciprodiazole[®]: 156 Ciprofloxacin Tablets & Metronidazole tablets).

A document describing the procedure of constitution of the randomization lists will be stored confidentially at Nagy Research CRO

Block size: 2, 4

The Randomization list will be done using website:
(<https://www.sealedenvelope.com/simple-randomiser/v1/lists>)

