10.7.6 Primary Safety analysis

A. Number of participants experiencing Serious Adverse Events (SAEs). [Time Frame: visit 1 to End of study visit].

- Frequency distribution (number & percent) of occurrence of SAEs necessitating a change or discontinuation of treatment. Chi² test will be used to determine *p*-value and significance between the 2 groups.
- Frequency distribution (number & percent) of type and severity of SAEs. Chi² test will be used to determine *p*-value and significance between the 2 groups.

B. Number of participants experiencing Adverse Events (AEs) leading to permanent discontinuation of the study drug. [Time Frame: visit 1 to End of study visit].

- Frequency distribution (number & percent) of causes of treatment discontinuations. Chi² test will be used to determine *p*-value and significance between the 2 groups.
- Frequency distribution (number & percent) of occurrence of AEs necessitating a change or discontinuation of treatment. Chi² test will be used to determine *p*-value and significance between the 2 groups.

- Frequency distribution (number & percent) of type and severity of AEs. Chi² test will be used to determine *p*-value and significance between the 2 groups.

10.7.7 Primary Efficacy analysis:

A. Complete resolution for Pelvi- abdominal infection based on pelvi-abdominal Ultrasound

- Frequency distribution (number & percent) of complete resolution for pelvi-abdominal infection. Chi² test will be used to determine *p*-value and significance between the 2 groups.

B. Complete healing of the post-operative wounds [Time Frame: Follow-up 1 V to End of study visit].

- Frequency distribution (number & percent) of complete healing of the post-operative wounds. Chi² test will be used to determine *p*-value and significance between the 2 groups.
- Frequency distribution (number & percent) of incomplete healing of the post-operative wounds. Chi² test will be used to determine *p*-value and significance between the 2 groups.
- Frequency distribution (number & percent) of no healing of the post-operative wounds. Chi² test will be used to determine *p*-value and significance between the 2 groups.

10.7.8 Secondary Safety analysis:

A. Presence of any signs/symptoms of post-operative wound infection such as redness, fever or wound discharge [Time Frame: visit 1 to End of study visit].

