8.3 Analyses variables

8.3.1 Descriptive Analysis:

- Descriptive analysis of the collected data. All enrolled patients will be included in the safety analysis.
- All quantitative primary and secondary end point variables will be described
- Data from primary and secondary endpoints will be summarized using appropriate summary statistics i.e. n (number of subjects), mean, Standard Deviation (SD), median and range.

8.3.2 Comparative Analysis:

- All tests will be performed on the 5% level of significance.
- Chi² test for unpaired categorical variables.
- Paired t-test to estimate the change in numerical variables throughout the study visits.
- Student t-test to estimate the comparison between the subgroups for the numerical variables.
- P-values less than 0.05 will be considered statistically significant

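### Two primary efficacy endpoints and primary safety are each tested at an unadjusted 5%, with no rule for what counts as efficacy success

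*Protocol*

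**What the plan says.** Protocol 10.3.1 and SAP 5.1 list one primary safety endpoint, the incidence of adverse events, and two primary efficacy endpoints: complete resolution of the infection, and "Complete healing of post-operative wounds".

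The primary analyses are in protocol 10.7.6 and 10.7.7, repeated in SAP 8.6 and 8.7. Safety has five bullets, resolution has one, and "Complete healing of the post-operative wounds [Time Frame: Follow-up 1 V to End of study visit" has three (complete, incomplete and no healing). Each bullet has its own chi-square test.

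The significance rule is the same for all of them. Protocol 10.7.3 says "All tests will be performed on the 5% level of significance", and SAP 8.3.2 adds "P-values less than 0.05 will be considered statistically significant".

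The sample-size section (protocol 10.5.1, SAP 7.1) gives "Design: non-inferiority", "Non-Inferiority margin = 2" (per cent), a 5% alpha of unstated sidedness, and one power figure, 80%. The only rates it cites are for clinical resolution: "Overall clinical resolution rates were statistically superior for CIP+MET (74%) compared with PIP/TAZO (63" per cent).

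Neither document states a success rule across the two efficacy endpoints, a testing order, an alpha split or a multiplicity adjustment.

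**The concern.** If resolution succeeds and wound healing does not, or the reverse, the plan does not say whether efficacy has been shown. That decision would be made after the results are known, in an open-label trial. The two possible rules have different operating characteristics: accepting either endpoint raises the false-positive risk, and requiring both lowers the power. The same gap affects safety, where five overlapping tests at 5% allow a single small p-value to be read as a primary safety difference.

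**Working it through.** **Inputs from the documents.** 156 per arm; alpha 5%; power 80%; margin 2 points; rates 63% and 74% (protocol 10.5.1). Primary bullets: 10.7.6 has 2 + 3, and 10.7.7 has 1 + 3, which makes 9.

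**1. Reproducing the plan's figure.** The non-inferiority formula is n per arm = (z for alpha + z for power)² × [pC(1 − pC) + pT(1 − pT)] / (pT − pC + margin)². Take control 63%, experimental 74% and one-sided 5%:

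(1.645 + 0.842)² × (0.2331 + 0.1924) / (0.11 + 0.02)² = 6.183 × 0.4255 / 0.0169 = 155.7, so 156 per arm and 312 in total.

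This matches exactly, with no allowance for dropout. At one-sided 2.5% the same inputs give 198 per arm. The 80% (80.1% when computed back) is therefore the power for one endpoint, at resolution rates, measured in all 156 per arm.

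**2. Either endpoint suffices.** For two independent tests with both null hypotheses true:
- 5% error in whatever direction counts (any difference, or the one-sided 5% that reproduces 312): 1 − 0.95² = 9.75%.
- Only the favourable tail of a two-sided 5% test counts: 1 − 0.975² = 4.94%.

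**3. Both endpoints required.**
- Independent tests with 80% power each: 0.80 × 0.80 = 64%.
- Same patients, positively correlated endpoints: between 64% and 80%.
- Separate patients: neither endpoint has 156 per arm. The documents do not give the split, so it is assumed here, with the same rates for both endpoints and no loss from the per-protocol restriction. Power = Φ(0.13 / √(0.4255/n) − 1.645).

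| Assumed split per arm | Power, endpoint 1 | Power, endpoint 2 | Joint power |
|---|---|---|---|
| 78 / 78 | 54.6% | 54.6% | 29.8% |
| 39 / 117 | 34.4% | 69.5% | 24.0% |

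**4. All nine bullets.** If they were independent, the chance of at least one p-value below 0.05 would be 1 − 0.95⁹ = 37.0%. They are not independent: the three healing categories divide one outcome, and the safety bullets overlap. The 37% is an illustration; the true figure cannot be derived from the documents.

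**5. Test against design.** The chi-square test addresses equality, not the 2-point margin. At 63% v 74% a two-sided 5% chi-square test has 55.3% power with 156 per arm and 31.4% with 78, so the stated 80% does not describe it either.

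**The case against.** Several stronger readings are tempting, and the documents do not support them.

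- *The two endpoints are in different patients.* This is not established. Protocol 10.1 describes the population as infection and/or post-operative treatment, while the synopsis design section and 10.5.2 say or. The objective (9.1.2) covers both non-operative and post-operative infection, and SAP Tables 9 and 10 head both endpoints with 156 per arm. Non-operative patients have no post-operative wound, so partial separation is likely, but its extent is unknown.
- *64% is the most the joint power can be.* It is not a ceiling. Overlapping patients with positively correlated endpoints can give up to 80%, while separate patients give far less than 64%, because the 80% being squared is no longer available.
- *Requiring both endpoints contradicts the stated 80%.* It does not. Protocol 10.5.1 gives that figure once, on resolution rates, and never offers it as joint power. The gap is that no joint figure exists.
- *Nine tests carry a 10% risk.* The 9.75% belongs to two efficacy tests under an either-endpoint rule.
- *The error exceeds 5% however success is defined.* It does not for the two efficacy tests if only the favourable tail of a two-sided test counts, which gives 4.9%. It is also fair to say that none of these figures is the false non-inferiority rate of the chi-square test, since that test does not assess non-inferiority.

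These points limit the size of the problem. They do not supply a success rule: both documents are silent on it, and the SAP repeats the protocol's analysis text.

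**Conclusion.** The concern holds in this limited form. The plan has two primary efficacy endpoints plus primary safety and nine primary chi-square bullets, each at an unadjusted 5%, and does not define efficacy success. Under an either-endpoint rule the false-positive risk for efficacy is up to 9.75%, assuming independence and 5% error in the direction that counts. Under a both-endpoints rule the 80% does not apply jointly, and how far power drops depends on patient overlap and correlation, neither of which the documents give. The 24% to 30% figures rest on assumed splits and equal rates and should be read as a range. The 80% itself also depends on the 11-point advantage used in the sample-size calculation.

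**What to change.** In protocol 10.7.3 and SAP 8.3.2:

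1. Set a fixed sequence applied to the planned non-inferiority comparison, meaning the confidence interval for the difference set against the margin at a stated one-sided alpha. Complete resolution comes first. Complete wound healing is confirmatory only if resolution succeeds.
2. Analyse each endpoint in the patients to whom it applies, give those denominators in SAP Tables 9 and 10, and state the margin for healing, since the single 2% is not tied to an endpoint.
3. State that the 80% power refers to the first endpoint only.
4. Report the remaining primary bullets (incomplete healing, no healing, adverse-event subtypes) descriptively, without significance claims.

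The cost is a short revision of the text and two table shells, with no new data. Protocol 10.7.2 already allows documented changes in the final SAP before database lock. The downside is that wound healing cannot be claimed if resolution fails. If the sponsor prefers to require both endpoints, no alpha adjustment is needed, but joint power must be stated, and that needs an assumption about the mix of infection and post-operative patients.

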10.7.4 Main criteria

- To compare safety of oral Ciprodiazole ® tablets (Ciprofolxacin/Metronidazole) versus currently used Ciprofloxacin Tablets & Metronidazole tablets in pelvi-abdominal infections, either non-operative or post-operative following IV antibiotics.
- To compare efficacy of oral Ciprodiazole ® tablets (Ciprofolxacin/Metronidazole) versus currently used Ciprofloxacin Tablets & Metronidazole tablets in pelvi-abdominal infections, either non-operative or post-operative following IV antibiotics.

10.7.5 Other criteria

- To describe presence of any signs/symptoms of post-operative wound infection such as redness, fever or wound discharge.
- To describe presence of undesirable effects on total leukocyte count and liver enzymes (SGOT & SGPT) between baseline (visit 1) to End of study visit (Follow up 2 V)
- To compare the complete resolution, improvement, failure or relapse of Pelvi- abdominal infection between ciprodiazole® versus combined treatment, based on pelvi-abdominal ultrasound and others
- To compare the number of days for complete healing of post-operative wounds between ciprodiazole® versus combined treatment

10.7.6 Primary Safety analysis

A. Number of participants experiencing Serious Adverse Events (SAEs). [Time Frame: visit 1 to End of study visit].

- Frequency distribution (number & percent) of occurrence of SAEs necessitating a change or discontinuation of treatment. Chi² test will be used to determine *p*-value and significance between the 2 groups.
- Frequency distribution (number & percent) of type and severity of SAEs. Chi² test will be used to determine *p*-value and significance between the 2 groups.

B. Number of participants experiencing Adverse Events (AEs) leading to permanent discontinuation of the study drug. [Time Frame: visit 1 to End of study visit].

- Frequency distribution (number & percent) of causes of treatment discontinuations. Chi² test will be used to determine *p*-value and significance between the 2 groups.
- Frequency distribution (number & percent) of occurrence of AEs necessitating a change or discontinuation of treatment. Chi² test will be used to determine *p*-value and significance between the 2 groups.

- Frequency distribution (number & percent) of type and severity of AEs. Chi² test will be used to determine *p*-value and significance between the 2 groups.

10.7.7 Primary Efficacy analysis:

A. Complete resolution for Pelvi- abdominal infection based on pelvi-abdominal Ultrasound

- Frequency distribution (number & percent) of complete resolution for pelvi-abdominal infection. Chi² test will be used to determine *p*-value and significance between the 2 groups.

B. Complete healing of the post-operative wounds [Time Frame: Follow-up 1 V to End of study visit].

- Frequency distribution (number & percent) of complete healing of the post-operative wounds. Chi² test will be used to determine *p*-value and significance between the 2 groups.
- Frequency distribution (number & percent) of incomplete healing of the post-operative wounds. Chi² test will be used to determine *p*-value and significance between the 2 groups.
- Frequency distribution (number & percent) of no healing of the post-operative wounds. Chi² test will be used to determine *p*-value and significance between the 2 groups.

10.7.8 Secondary Safety analysis:

A. Presence of any signs/symptoms of post-operative wound infection such as redness, fever or wound discharge [Time Frame: visit 1 to End of study visit].

Frequency distribution (number & percent) of presence of any signs/symptoms of post-operative wound infection such as redness, fever or wound discharge. Chi² test will be used to determine *p*-value and significance between the 2 groups.

B. Change in Total leukocytes count between baseline (visit 1) to End of study visit

Descriptive analysis (mean, Standard Deviation, Median, Interquartile Range, Minimum and Maximum) of total leucocyte will be from baseline (visit 1) to End of study visit. Percent change will be calculated between baseline to End of study. Paired t-test will be used to determine *p*-value and significance between baseline and at the end of the study. Unpaired t-test will be used to determine the *p*-value and significance between Changes in total leucocyte between 2 groups.

C. Change in Liver enzymes (SGOT) between baseline (visit 1) to End of study visit

Descriptive analysis (mean, Standard Deviation, Median, Interquartile Range, Minimum and Maximum) of Liver enzymes (SGOT) will be from baseline (visit 1) to End of study visit. Percent change will be calculated between baseline to End of study. Paired t-test will be used to determine *p*-value and significance between baseline and at the end of the study. Unpaired t-test will be used to determine the *p*-value and significance between Changes in Liver enzymes (SGOT) between 2 groups.

D. Change in Liver enzymes (SGPT) between baseline (visit 1) to End of study visit

Descriptive analysis (mean, Standard Deviation, Median, Interquartile Range, Minimum and Maximum) of Liver enzymes (SGPT) will be from baseline (visit 1) to End of study visit. Percent change will be calculated between baseline to End of study. Paired t-test will be used to determine *p*-value and significance between baseline and at the end of the study. Unpaired t-test will be used to determine the *p*-value and significance between Changes in Liver enzymes (SGPT) between 2 groups.

10.7.9 Secondary Efficacy analysis:

A. Complete resolution, improvement, failure or relapse of Pelvi- abdominal infection

- Frequency distribution (number & percent) of complete resolution, improvement, failure or relapse for Pelvi- abdominal infection. Chi² test will be used to determine *p*-value and significance between the 2 groups.
- Frequency distribution (number & percent) of improvement for Pelvi- abdominal infection. Chi² test will be used to determine *p*-value and significance between the 2 groups.
- Frequency distribution (number & percent) of failure for Pelvi- abdominal infection. Chi² test will be used to determine *p*-value and significance between the 2 groups.
- Frequency distribution (number & percent) of relapse for Pelvi- abdominal infection. Chi² test will be used to determine *p*-value and significance between the 2 groups.

B. Days for complete healing of post-operative wounds after 8 days of treatment (Follow up 1 visit) & 15 days of treatment (Follow up 2 visit or End of study visit)

Descriptive analysis (mean, Standard Deviation, Median, Interquartile Range, Minimum and Maximum) of days for complete healing versus combined treatment will be after 8 days of treatment (Follow-up 1 V) & 15 days of treatment (End of study visit). Percent change will be calculated between baseline to End of study. Paired t-test will be used to determine *p*-value and significance between baseline and at the end of the study. Unpaired t-test will be used to determine the *p*-value and significance between Changes in complete healing between 2 groups.

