8.6 Primary Safety analysis

A. Number of participants experiencing Serious Adverse Events (SAEs). [Time Frame: visit 1 to End of study visit].

- Frequency distribution (number & percent) of occurrence of SAEs necessitating a change or discontinuation of treatment. Chi² test will be used to determine p-value and significance between the 2 groups.

- Frequency distribution (number & percent) of type and severity of SAEs. Chi² test will be used to determine *p*-value and significance between the 2 groups.

B. Number of participants experiencing Adverse Events (AEs) leading to permanent discontinuation of the study drug. [Time Frame: visit 1 to End of study visit].

- Frequency distribution (number & percent) of causes of treatment discontinuations. Chi² test will be used to determine *p*-value and significance between the 2 groups.
- Frequency distribution (number & percent) of occurrence of AEs necessitating a change or discontinuation of treatment. Chi² test will be used to determine *p*-value and significance between the 2 groups.
- Frequency distribution (number & percent) of type and severity of AEs. Chi² test will be used to determine *p*-value and significance between the 2 groups.

8.7 Primary Efficacy analysis:

A. Complete resolution for Pelvi- abdominal infection based on pelvi-abdominal Ultrasound

- Frequency distribution (number & percent) of complete resolution for pelvi-abdominal infection. Chi² test will be used to determine *p*-value and significance between the 2 groups.

B. Complete healing of the post-operative wounds [Time Frame: Follow-up 1 V to End of study visit].

- Frequency distribution (number & percent) of complete healing of the post-operative wounds. Chi² test will be used to determine *p*-value and significance between the 2 groups.
- Frequency distribution (number & percent) of incomplete healing of the post-operative wounds. Chi² test will be used to determine *p*-value and significance between the 2 groups.
- Frequency distribution (number & percent) of no healing of the post-operative wounds. Chi² test will be used to determine *p*-value and significance between the 2 groups.

8.8 Secondary Safety analysis:

A. Presence of any signs/symptoms of post-operative wound infection such as redness, fever or wound discharge [Time Frame: visit 1 to End of study visit].

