9.4 Primary End Point

9.4.1 Primary Safety

Table 4 *Number and percent of Adverse Event necessitating a change or discontinuation of treatment among treatment groups*

	Group A (N=156)	Group B (N=156)	p-value
Total No of SAE, N (%)			
SAE1, N (%)			
SAE2, N (%)			
SAE3, N (%)			

Table 5 *Number and percent of Serious Adverse Event among treatment groups*

	Group A (N=156)	Group B (N=156)	p-value
Total No of SAE, N (%)			
SAE1, N (%)			
SAE2, N (%)			
SAE3, N (%)			

Table 6 *Number and percent of causes of treatment discontinuations among treatment groups*

	Group A (N=156)	Group B (N=156)	p-value
Total No of treatment discontinuations, N (%)			
Cause1, N (%)			
Cause2, N (%)			
Cause3, N (%)			

Table 7 *Number and percent of Adverse Event necessitating a change or discontinuation of treatment among treatment groups*

	Group A (N=156)	Group B (N=156)	p-value
Total No of AE, N (%)			
AE1, N (%)			
AE2, N (%)			
AE3, N (%)			

Table 8 *Number and percent of Adverse Event among treatment groups*

	Group A (N=156)	Group B (N=156)	p-value
Total No of AE, N (%)			
AE1, N (%)			
AE2, N (%)			
AE3, N (%)			

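### The primary safety analysis pre-specifies no between-arm difference or confidence interval, so it does not state what excess harm the data exclude

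*Protocol*

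**What the plan says.** The primary safety endpoint in protocol 10.3.1 is "Incidence of serious/non-serious adverse events". The sample-size text in protocol 10.5.1 opens with "As the primary objective is to assess the safety of oral Ciprodiazole".

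Protocol 10.7.6 and SAP 8.6 put the analysis under two headings, one for SAEs ("Number of participants experiencing Serious Adverse Events (SAEs). [Time Frame: visit 1 to End of study visit") and one for AEs leading to permanent discontinuation. The items beneath them are frequency distributions, for example "Frequency distribution (number & percent) of type and severity of SAEs". Each ends with a chi-square test that "will be used to determine p-value and significance between the 2 groups". The inferential rule in SAP 8.3.2 is "P-values less than 0.05 will be considered statistically significant".

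The table shells match. SAP Table 5, "Number and percent of Serious Adverse Event among treatment groups", has columns for Group A, Group B and p-value, and its first row is "Total No of SAE, N" with a percentage. Tables 4 and 6 to 8 have the same columns.

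Protocol 14.2 adds AE tabulations by body system, preferred term, intensity, seriousness and causality. These are descriptive. A 95% confidence level appears only among the sample-size parameters.

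**The concern.** The two arms receive the same two active substances under a design labelled non-inferiority, so the natural safety claim is that the combined tablet is no worse. A chi-square p-value above 0.05 does not support that claim. It shows only that a difference was not demonstrated, which is expected when events are few, whether or not there is excess harm. An interval for the difference, computed from the same data, shows how large an excess remains compatible with the results. Without it, the pre-specified reading of the primary safety result rests on a threshold that cannot tell good evidence of similarity from sparse data.

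**Working it through.** **Inputs.** 156 per arm (protocol 10.5.1 and 10.5.2). Tests at 5% (protocol 10.7.3), taken as two-sided because a chi-square test is planned. The documents give no AE or SAE rate, so the rates and counts in steps 2 and 3 are assumptions.

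**Step 1. Does the planned size carry information about safety?** The stated total of 312 is reproduced by

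n per arm = (z0.95 + z0.80)² × [0.63 × 0.37 + 0.74 × 0.26] / (0.74 − 0.63 + 0.02)² = 6.183 × 0.4255 / 0.0169 = 155.7, rounded up to 156.

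This is a one-sided 5% calculation; one-sided 2.5% gives 198 per arm. The inputs are clinical resolution rates of 63% and 74% and the 2-point margin. The 312 therefore gives no assurance about power for adverse events.

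**Step 2. Power to detect a doubling.** Exact power is the sum of Bin(x; 156, p1) × Bin(y; 156, p2) over all pairs (x, y) for which the uncorrected chi-square, d² / [p̄(1 − p̄)(2/156)], exceeds 3.841.

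| Assumed risks | Exact power |
|---|---|
| 1% v 2% | 10% |
| 2% v 4% | 16% |
| 5% v 10% | 38% |
| 10% v 20% | 70% |
| 20% v 40% | 97% |

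Normal-approximation check at 2% v 4%: SE0 = √(2 × 0.03 × 0.97/156) = 0.01931 and SE1 = √((0.0196 + 0.0384)/156) = 0.01928. Power = Φ((0.02 − 1.96 × 0.01931)/0.01928) = Φ(−0.93), about 18%.

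**Step 3. What an interval adds.** Newcombe's method combines the Wilson limits (l, u) of each arm:
- lower = d − √[(p1 − l1)² + (u2 − p2)²]
- upper = d + √[(u1 − p1)² + (p2 − l2)²]

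For 6 v 3 of 156: p1 = 3.85% (Wilson 1.77 to 8.14), p2 = 1.92% (0.66 to 5.50), d = 1.92 points.
- Lower = 1.92 − √(2.07² + 3.58²) = 1.92 − 4.13 = −2.2
- Upper = 1.92 + √(4.29² + 1.27²) = 1.92 + 4.47 = +6.4
- Chi-square 1.03, p = 0.31

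| Patients with event (Ciprodiazole v control) | Difference, points | 95% interval, points | Chi-square p |
|---|---|---|---|
| 0 v 0 | 0.0 | −2.4 to +2.4 | undefined |
| 3 v 3 | 0.0 | −3.8 to +3.8 | 1.00 |
| 6 v 3 | +1.9 | −2.2 to +6.4 | 0.31 |
| 8 v 3 | +3.2 | −1.2 to +8.0 | 0.12 |
| 40 v 31 | +5.8 | −3.6 to +15.0 | 0.22 |

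None of these reaches p < 0.05, yet the largest compatible excess runs from 2.4 to 15 points. With fewer than 10 events in total, the expected count in each event cell is below 5 (9/2 = 4.5 for 6 v 3), and no exact test is planned.

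**Step 4. Can the interval be computed from the shells as drawn?** Not cleanly.
- Rows labelled as a total number of SAEs or AEs may count events rather than participants.
- Table 4 is titled for adverse events but its rows are SAEs.
- The denominator is given as all patients with at least one dose (protocol 10.7.1, SAP 8.1), all enrolled patients (protocol 10.7.3, SAP 8.3.1), and an intention-to-treat set needing a baseline and a post-baseline visit (protocol 14.2). The shells fix N at 156 per arm.

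**The case against.** The strongest reply is that percentages per arm are planned, so any reader can derive a difference and an interval, and protocol 14.2 tabulates harms in more detail. That is right as far as it goes. A reader might infer that the trial cannot quantify harm, or that significance is its only safety output; the documents do not support either. What stands is that the sponsor's own pre-specified conclusion rests on the p-value, and the effect measure, interval method and denominator would be chosen after the data are seen.

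Second, low power depends on assumed rates, and the endpoint covers all AEs, not only serious ones. This also stands. It is tempting to say that a doubling of harm would usually be missed, but step 2 shows that this holds only for rare events. The missing estimate itself does not depend on any assumed rate.

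Third, the primary efficacy analysis has the same number, percent and p-value form. That is true, but an interval added there would leave protocol 10.7.6, SAP 8.6 and Tables 4 to 8 unchanged.

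Finally, a reader might infer either that no safety margin exists or that the 2% margin is one. Protocol 10.5.1 and SAP 7.1 introduce the margin under the safety objective, support it with resolution rates and name no endpoint. Neither inference is secure.

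**Conclusion.** The concern holds as a gap in what is pre-specified. The primary safety comparison has no planned effect estimate or interval, and its stated rule, p below 0.05, cannot support a conclusion of no worse safety. The consequence is largest for SAEs if they are rare: under assumed control risks of 1% to 5%, exact power to detect a doubling is 10% to 38%. For common AEs it is much smaller, with 70% power at 10% v 20% and 97% at 20% v 40%.

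The endpoint of the 2% margin should be settled, because it affects what an interval could show. With no events in either arm, the Newcombe upper limit is z²/(n + z²). The two-sided 95% limit is 3.84/159.84 = 2.4 points, above 2. At the one-sided 5% level that reproduces 312, it is 2.71/158.71 = 1.7 points. If the margin were meant for safety, the outcome could turn on an interval level that the documents do not specify.

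This is a worthwhile and inexpensive improvement. It does not make the trial data unusable.

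**What to change.** In protocol 10.7.6, SAP 8.6 and SAP Tables 4 to 8:

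- For participants with any SAE, any AE, and any AE leading to discontinuation, report the difference in proportions (Ciprodiazole minus control) with a 95% Newcombe or Miettinen-Nurminen interval.
- Word the safety conclusion by the excess that the interval excludes, not by p above 0.05.
- State whether the 2% margin applies to safety. If it does not, say that no safety margin is set.
- Count participants rather than events, and align the title and rows of Table 4.
- Use one safety denominator, reconciling protocol 10.7.1, 10.7.3 and 14.2, and replace the fixed 156 with the actual number in that population.

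The cost is SAP wording and revised shells for five tables, somewhat more than one added column because the rows and denominators must be settled first. The safety conclusion may also read less favourably than a non-significant p-value would. No new data are needed, and protocol 10.7.2 already provides for a final SAP before database lock.
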